## VERSION HISTORY

Version:	Version Date:	Changes:
0.1	4 August 2021	Original version
0.2	28 April 2022	Updated contacted information for trial team. Removed the ADQ outcome Included additional exploratory analysis excluding participants recruited during COVID.
0.3	4 May 2022	Updated in inclusion/exclusion criteria and updated model used in the primary analysis to reflect the current version of the protocol. Updated safety analysis section with details regarding reporting of adverse events and adverse reactions.
0.4	19 May 2022	Explicated stated the family and the link function to use for the primary analysis. Including time in the study (years) to be adjusted for in the analysis models as participants recruited earlier will have a longer study duration and thus possibly higher re-prescription rates and hospital admission, or in the very least, more time in which these events can occur.
0.5	10 November 2022	Updated definition of the primary outcome
0.6	22 June 2023	Updated definition of the primary outcome
0.7	19 December 2023	Updated several sections of the SAP to align with version 13.0 of the protocol
0.8	19 February 2024	Updated the SAP to align with version 14.0 of the protocol and [name]'s comments
0.9	26 February 2024	Updated the SAP in response to UG and NW comments
0.10	1 March 2024	Updated the SAP in response to UGs comments
0.11	15 March 2024	Updated the SAP in response to the trial teams comments from the meeting on the 11 March 2024. Sensitivity analysis regarding excluding participants recruited over COVID removed.
0.12	22 March 2024	Updated the SAP in response to UG and NW comments
0.13	22 March 2024	Corrected typo
0.14	5 April 2024	Responded to the CI comments
1.0	9 April 2024	Signed off

## 1 INTRODUCTION

**Trial title:** Penicillin allergy status and its effect on antibiotic prescribing, patient outcomes, and antimicrobial resistance

**Short title:** ALABAMA: Allergy antibiotics and microbial resistance

**Ethics Ref:** 19/LO/0176

**Sponsor:** University of Leeds

**Funder:** National Institute for Health Research (NIHR)

**Protocol Data and Version No.:** 16 November 2023, version 14.0

### 1.2 PURPOSE AND SCOPE OF THE PLAN

This document details the proposed analysis of the main papers reporting results for the National Institute for Health Research (NIHR) funded randomised controlled trial to determine whether the PAAP intervention is clinically effective in improving antibiotic prescribing, patient outcomes and de-labelling. The results reported in these papers should follow the strategy described here. Subsequent analyses of a more exploratory nature will not be bound by this strategy, though they are expected to follow the broad principles laid down here. The principles are not intended to curtail exploratory analysis (for example, to decide cut-point for categorisation of continuous variables), nor to prohibit accepted practices (for example, data transformation prior to analysis), but they are intended to establish the rules that will be followed, as closely as possible, when analysing and reporting the trial.

The analysis strategy will be available on request when the principal papers are submitted for publication in a journal and uploaded in advance of analysis to clinicaltrials.gov submission NCT04108637. Suggestions for subsequent analyses by journal editors or referees, will be considered carefully, and carried out as far as possible in line with the principles of this analysis strategy; if reported, the source of the suggestion will be acknowledged.

Any deviations from this statistical analysis plan will be described and justified in the final report of the trial. This analysis should be carried out by an identified, appropriately qualified, and experienced statistician, who should ensure the integrity of the data during their processing. Examples of such procedures include quality control and evaluation procedures.

## 1.3 TRIAL OVERVIEW

The importance of antimicrobial resistance (AMR) and the need to reduce its impact is well recognised (Davies 2013). Penicillins are the most commonly prescribed antibiotics (Public Health England 2017) and remain the first-line therapy for many common infections. A record of penicillin allergy has a marked effect on antibiotic prescribing (Solensky et al. 2000; Salkind et al. 2001; McLean-Tooke et al. 2011; Blumenthal et al. 2018; West et al 2019). Penicillin allergy records are common because side effects and symptoms related to the infection requiring antibiotic treatment are often mislabelled as allergies. About 6-10% of the UK population self-report a penicillin allergy but, importantly, fewer than 10% of these patients are truly allergic (NICE 2014; West et al 2019). Consequently, a significant proportion of the population are potentially restricted access to highly effective penicillins. Penicillin allergy records are associated with AMR; evidence from the UK and USA suggests that patients with a penicillin allergy record are more likely to acquire multi-drug resistant bacteria, including meticillin-resistant *Staphylococcus aureus* (MRSA) (Reddy et al. 2013; Macy & Contreras 2014; Blumenthal et al. 2018; West et al. 2019).

The focus of ALABAMA is 'false positive' records of penicillin allergy, how these affect prescribing and whether a complex intervention aimed at correcting inaccurate records is clinically/cost effective. Patients with a penicillin allergy are usually not prescribed penicillins but instead receive alternative, broad-spectrum antibiotics which may lead to suboptimal therapy, be associated with poorer longer-term outcomes, and contribute to AMR (Charneski et al. 2011; Currie et al. 2014; Blumenthal et al. 2018; West et al 2019). Our preliminary research found macrolide, tetracycline, cephalosporin, quinolone, and clindamycin prescribing were all more common in patients with a record of penicillin allergy compared to those without, and that antibiotic prescriptions were almost twice as frequent in patients with a penicillin-allergy record (West et al. 2019). These differences were not explained by age, sex, or comorbidity. Systematic review evidence indicates that antibiotic-allergies affect health outcomes, increasing mortality, length of stay, and costs (Krah et al 2021 (<https://www.ncbi.nlm.nih.gov/pubmed/33059777>)). The large discrepancy between reported and true allergy rates suggests that introducing a 'pre-emptive' penicillin allergy assessment pathway (PAAP) for patients who are more likely to receive antibiotics, could impact upon antibiotic prescribing, yield patient benefits, limit AMR/Healthcare associated infection (HCAI), and deliver NHS cost savings.

Assessment of patients with penicillin allergy in specialist clinics is already provided within the NHS, but most who are eligible are not offered the service because of a lack of capacity (Krishna et al. 2017). Currently, penicillin allergy testing in many immunology/allergy clinics is performed over at least two clinic visits; the first, to undertake history and perform skin testing (ST); the second to assess reactions and undertake oral challenge testing (OCT) followed by communication of results. The allergy history is important to determine if the allergy history is spurious, of uncertain risk, low risk, or high risk of true penicillin allergy (Krishna et al. 2014). Skin testing and OCT may follow.

The ALABAMA trial approach will be different from this standard NHS practice in two ways:

- 1) Streamlining the process by undertaking initial elements (history) in the community/via telephone, and developing a "one stop shop" single hospital clinic visit for assessment (skin testing and/or OCT)
- 2) Pre-emptive testing will be undertaken in patients with a higher risk of being prescribed antibiotics in primary care, rather than in the context of an acute allergic reaction or soon after a reaction

If the evaluation finds that this more 'patient-friendly' approach to allergy testing is more efficient, this would enable more patients to be tested within current resources. This proposed trial testing will take place in an hospital clinic but testing could be undertaken by appropriately trained staff in all units with facilities to deal with severe allergic reactions. It is important to note that pre-emptive allergy testing as outlined in the ALABAMA PAAP is different from testing a patient who has an absolute need for a penicillin to treat a life-threatening

infection. The risk-benefit analysis is different in these two situations and a more cautious approach has been taken in the ALABAMA PAAP.

PAAP has deliberately been designed as an efficient one-stop procedure that will involve [1] medical history in primary care to either [i] exclude those at risk of anaphylaxis or other severe adverse reactions, or [ii] indicate a referral to secondary care and [2] half a day in clinic and potentially a three-day post clinic course of oral antibiotics. The PAAP differs from current standard UK and European guidelines in that it offers patients assessed as 'low risk' of true allergy an abbreviated test consisting of direct oral challenge, with no preceding skin tests. Whilst the gold standard test with which to establish tolerance to penicillin is an oral challenge, current UK and European guidelines advise that patients should first be skin tested, using prick or intradermal tests, or both, although there is now recognition that this is not needed for lower risk patients (Savic et al 2022) (<https://www.ncbi.nlm.nih.gov/pubmed/36128691>). Skin testing identifies patients who are IgE-sensitised, and provides risk stratification for progression to a challenge test, for those with higher risk histories. Skin tests have a negative predictive value (NPV) approaching 100%, and patients who do not react to prick or intradermal tests are therefore unlikely to have a severe reaction on challenge. However, the interpretation of positive skin tests is less clear; these patients are generally not offered a challenge test and so the positive predictive value (PPV) is hard to determine. The PPV is generally accepted to be less than 50% based on a limited number of prospective studies, and on outcomes from accidental re-exposure. Increasingly, the evidence demonstrates that patients can be risk stratified for a challenge test on the basis of history alone. Where symptoms are not severe, not suggestive of an IgE-mediated reaction, are vague, or historic, the utility of skin testing is low and a direct oral challenge may be safe and appropriate. This approach is already used routinely for children in the UK and several studies have demonstrated safety and efficacy in adults. Patients whose histories are not clearly low risk will still undergo skin testing, and only proceed to oral challenge if this is negative.

The PAAP will be divided into three stages which can initially be undertaken in a primary care setting but move to a hospital clinical setting for more complex testing. Each stage has been risk assessed based on published data and expert opinion to minimise risk of harm and keep the costs of the pathway down.

## 1.4 OBJECTIVES

All the study objectives are described below. A full summary of the study objectives and outcome measures can be found in Appendix I (section 13.1), and the current version of the protocol (version 14.0).

### 1.4.1 PRIMARY OBJECTIVE

The primary objective is to determine the effect of PAAP on penicillin prescribing.

### 1.4.2 SECONDARY OBJECTIVES

- 1) To determine whether the PAAP intervention is clinically effective in improving treatment response failure,
- 2) Effects of PAAP on symptom duration,
- 3) Effects of PAAP on total antibiotic prescribing,
- 4) Effects of PAAP on hospital admissions and length of hospital stays (safety outcomes),
- 5) Effects of PAAP on mortality rates (safety outcome),
- 6) Effects of PAAP on Meticillin-resistant *Staphylococcus aureus* (MRSA) infection/colonisation,
- 7) Effects of PAAP on *Clostridioides difficile* infection,

- 8) To explore patient and clinical views and experiences of penicillin allergy testing, test results, and future antibiotic use,
- 9) (Process evaluation) To explore patient and clinician experiences of trial procedures,
- 10) To measure the influences on clinician and patient behaviour change regarding prescribing and consuming penicillin following a negative test result,
- 11) Cost effectiveness for the PAAP intervention compared to usual care,
- 12) Effects of PAAP on de-labelling:
  - a) at 3 months post randomisation,
  - b) up to 12 months post randomisation.
- 13) Additional safety outcomes (exploratory outcome)
- 14) Effects of PAAP on all outcomes for follow up post 12 months.

N.B. Objectives 8, 9, 10, and 11 will be analysed as part of the qualitative, economic, and process evaluation and will be reported separately from the main statistical analysis report.

## **2 TRIAL DESIGN**

This is a multicentre, two parallel-arm, open label, individually randomised pragmatic trial with a nested pilot trial.

Potential participants who met the eligibility criteria were identified during a search of their electronic health records at their general practice. The electronic search criteria were developed centrally by the research team in partnership with TPP and made available for running locally on SystmOne e.g. by practice managers, Local Clinical Research Network (LCRN) Research Nurse Team, or Leeds CCG Pharmacy Technician team. Potential participants were sent an invitation pack and those interested in taking part returned an expression of interest form to the trial team. They were telephoned and booked into an either a face to face, or telephone appointment with their GP or Research Nurse at a time that was convenient to them. During this appointment, their GP or a delegated member of the staff confirmed their eligibility to participate and consented them to take part in the trial. The participants then received another telephone call from a member of the trial team to complete the baseline case report form (CRF). At this point, the participants were asked if they had taken any antibiotics in the previous two weeks; if they had, the randomised/baseline call will be postponed until the participant has been free of antibiotic use for two weeks.

Once the baseline CRF was complete the participants were randomised to usual care or the PAAP intervention arm. Those randomised to the PAAP intervention arm were booked into an appointment at the clinic where they had penicillin allergy testing.

Participants recruited during the nested pilot phase were followed up for an initial 4 months for the feasibility outcomes, during which they were contacted monthly by the trial team. Following a “stop go” assessment, all nested pilot study participants were subsequently followed up for at least 12 months in the main trial to align their follow-up with participants recruited to the main trial.

Regular reports were run in the ALABAMA unit to identify participants who had been prescribed an antibiotic, for any cause, in the previous 7 days. A member of the research team sent an alert to the trial research nurses team who then followed the participant up for the duration of the associated infection. The research team then designated an antibiotic prescription as a ‘primary event’ if the patient was prescribed an antibiotic for a pre-defined list of infections (see Appendix II). Participants receiving antibiotics for a primary event, were asked to complete a symptom diary. At the end of the follow up period their electronic health records were reviewed to ensure we had captured all antibiotic events. All trial participants had case note review and, if required had capture hospital episode statistics, and mortality data.

Throughout this process general practice staff and participants received behaviour change intervention materials.

See Appendix III for study flowchart.

## **2.1 OUTCOME MEASURES**

A summary of the study objectives can be found in section 1.4. An outline of the trial procedures and time points can be found in Appendix IV. Only the outcomes which pertain to this statistical analysis plan will be listed here.

### **2.1.1 PRIMARY OUTCOME – EFFECTS OF PAAP ON PENICILLIN PRESCRIBING**

The primary outcome is the effect of PAAP on penicillin prescribing, and is defined as: the proportion of participants who receive prescriptions for a penicillin when attending for predefined conditions where a penicillin is the first-line recommended antibiotic (see Appendix II) up to 12 months post-randomisation.

The primary outcome will be coded as 1 (“Yes”) if there is evidence of a penicillin prescription during the course of routine care, up to 12 months post randomisation on any of the following data sources: SystmOne report/notes review (Variable *ISPRIMARYEVENT*), patient follow-up calls, or hospital prescribing reports. Participants that have not required penicillin treatment during the trial will have their primary outcome coded as 0 (“No”).

Participants who do not have evidence of a prescription and who withdrew consent for notes review to be conducted, will have their primary outcome missing at 12 months.

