## 2.3 SAMPLE SIZE

The primary outcome was initially treatment response failure defined as the percentage of re-prescription of an alternative antimicrobial within 28 days of an index prescription. A total sample size between 1592 and 2090 participants provided 80-90% power to detect a clinically important absolute difference of 7.9% in re-prescription rate at one year between groups (i.e. reducing from 19.8% in the control group to 11.9% in the PAAP group) at 5% level of significance (2-sided). The sample size had been adjusted assuming 50% of participants will require at least one prescription within 1 year from randomisation and allowing for 10% dropout. Participants are classed as enrolled at the point of randomisation.

The primary outcome was then changed to 'effects of PAAP on penicillin prescribing', defined as 'The proportion of participants who receive prescriptions for a penicillin attending for predefined conditions where a penicillin is the first-line recommended antibiotic (see Appendix II) during the course of routine primary care up to 12 months post randomisation. A total sample of 848 (i.e. 424 per group) was required to provide 90% power to detect an increase in the proportion of penicillin prescription from 4% (Usual Care) to 14% (PAAP) over the year after randomisation at 5% level of significance (2-sided) and 10% attrition. The sample size has been adjusted assuming 50% of participants will require at least one prescription within 1 year from randomisation. At 80% power, the sample size required was 656 (i.e. 328 per group). The table below also provides the sample size required if not all participants have reached 12 months follow-up.

Power	% Difference	Total sample size (all reached 12 months FU)	Total sample size (80% reached 12 months FU)	Total sample size (90% reached 12 months FU)
80%	10%	656	820	729
	15%	372	465	413
90%	10%	848	1060	942
	15%	472	590	524

Results from our recent analysis, using data extracted from the SystmOne database, suggested that there were an average of 110 patients per average practice size of 6000 who fulfilled our inclusion criteria.

- 1) Adults (over 18 years),
- 2) Penicillin allergy in electronic health records,
- 3) And in receipt of a penicillin, cephalosporin, tetracycline, quinolone, or macrolide class antimicrobial in the previous 24 months.

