### 4.1 PRIMARY OUTCOME

The primary outcome is penicillin prescribing, defined as the proportion of participants who receive prescriptions for a penicillin when attending for predefined conditions where a penicillin is the first-line recommended antibiotic up to 12 months post-randomisation. A binomial mixed-effects generalised linear model (MEGLM) with a logit link function will be fitted to the data with penicillin prescribing within 12 months of randomisation, as the dependent variable. The model will include randomised group, age, number of antibiotic prescriptions (as a continuous variable) up to the 24 months prior to randomisation (up to 12 months for those recruited to the nested pilot study), and the number of QOF registered diseases as fixed effects. These variables will come from the clinical database. GP practice will be included as a random effect. The adjusted relative risk between the randomised groups and the corresponding 95% confidence intervals will be obtained from the marginal adjusted relative risk (based on delta-method standard errors (Norton et al. 2013)) between the randomised groups and reported alongside the associated P-value.

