## **14.2 APPENDIX II. COMMON INFECTIONS MANAGED IN THE COMMUNITY FOR WHICH A PENICILLIN IS THE FIRST LINE RECOMMENDED THERAPY**

ALABAMA Infections for which an antibiotic prescription would be considered a primary event, and subsequently assessed for primary trial outcome:

- Acute sore throat, pharyngitis, tonsillitis,
- Oral infection,
- Parotitis, salivary gland infection,
- Community acquired pneumonia,
- Chest infections i.e. 'acute bronchitis' or 'lower respiratory infection' or unspecified,
- Acute otitis media,
- Acute bacterial rhinosinusitis,
- Infective COPD exacerbation: amoxicillin or doxycycline first line unless patient at higher risk of treatment failure then co-amoxiclav; empirical treatment or guided by most recent sputum culture and susceptibilities,
- Acute exacerbation of bronchiectasis,
- Skin and soft tissue infection (cellulitis, surgical wound infection, infected ulcer/pressure sore, erysipelas, boil, furuncle, impetigo, etc.),
- Diverticulitis,
- Dental abscesses.

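### The primary-outcome coding rule does not carry the listed-infection condition to every source, so followed as written it can count a penicillin that the definition excludes

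*SAP*

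**What the plan says.** SAP section 2.1.1 defines the primary outcome as "the proportion of participants who receive prescriptions for a penicillin when attending for predefined conditions where a penicillin is the first-line recommended antibiotic", with the conditions listed in Appendix II and a 12-month window. Section 4.1, which specifies the primary model, repeats this: participants who "receive prescriptions for a penicillin when attending for predefined conditions where a penicillin is the first-line recommended antibiotic up to 12 months post-randomisation". Appendix I agrees.

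The next paragraph of 2.1.1 turns the definition into codes:

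- **Code 1:** "evidence of a penicillin prescription during the course of routine care, up to 12 months post randomisation on any of the following data sources". The sources are the SystmOne report or notes review (with ISPRIMARYEVENT named beside it), "patient follow-up calls, or hospital prescribing reports".
- **Code 0:** "Participants that have not required penicillin treatment during the trial will have their primary outcome coded as 0".
- **Missing:** no evidence of a prescription, and consent for notes review withdrawn.

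Section 2 says that a prescription becomes a primary event "if the patient was prescribed an antibiotic for a pre-defined list of infections". Appendix II introduces its list as "Infections for which an antibiotic prescription would be considered a primary event, and subsequently assessed for primary trial outcome". Neither limits the term to penicillins.

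On care setting, section 2.3 describes the outcome as arising "during the course of routine primary care up to 12 months post randomisation", whereas 2.1.1 speaks of routine care generally and adds hospital prescribing.

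**The concern.** The definition has two conditions, drug and infection. The coding rule states only the drug. The infection enters solely through a variable attached to one of the three sources, and the rule never says that both conditions must hold for the same prescription.

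This variable feeds the trial's single confirmatory test. A penicillin given for an unlisted infection says something about prescribing after allergy testing, but it is not the outcome defined or the one on which the sample size was built. Including such prescriptions would move the relative risk by an amount that depends on how common they are and whether they differ by arm. The section 11 validation by a second statistician also needs one rule to check against.

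The rule for 0 has three weaknesses. It speaks of penicillin being required, not received. It refers to the whole trial, although data after 12 months are collected (Objective 14). It does not clearly cover a listed infection treated with a non-penicillin, which is the behaviour that the intervention aims to change.

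**Working it through.** **1. Definition and coding rule compared by type of participant** (notes review available, events within 12 months)

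| Participant | By definition | By the coding rule as written |
|---|---|---|
| Penicillin for a listed infection | 1 | 1 |
| Penicillin for an unlisted infection only, found in a hospital report | 0 | 1 |
| Penicillin for an unlisted infection only, mentioned on a follow-up call | 0 | 1, unless the call is one tied to a listed infection |
| Listed infection treated with a non-penicillin only | 0 | Not 1; not clearly within the wording for 0; not missing |
| No antibiotic | 0 | 0 |

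On calls, Appendix I ties the post-antibiotic contacts to predefined conditions. Section 2.1.1 says only follow-up calls, and the schedule in Appendix IV has others (pilot monthly calls, the 12-month call). The gap is therefore clearest for hospital reports and partial for calls.

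**2. Reproducing the plan's sample size**

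Inputs from section 2.3: 4% v 14%, two-sided 5%, 50% with at least one prescription, 10% attrition.

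With pooled rate 0.09, before continuity correction:

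n = [1.96·√(2 × 0.09 × 0.91) + 1.2816·√(0.04 × 0.96 + 0.14 × 0.86)]² / 0.10² ≈ 170.0

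With continuity correction:

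n′ = (n/4)·[1 + √(1 + 4/(n × 0.10))]² ≈ 189.5, so 190 per arm

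190 / 0.5 / 0.9 = 422.2, so 423 per arm and 846 in total, against 848 stated. At 80% power the same steps give 147 per arm, then 327 and 654, against 656 stated. The plan's figures reproduce to within rounding.

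The division by 0.5 shows that 4% v 14% applies to the half with an event. Among all randomised this is 0.5 × 4% = 2% v 0.5 × 14% = 7%, a relative risk of 3.5.

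**3. Effect of counting penicillins for unlisted infections**

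The SAP gives no rate for these, so the added rate q is an assumption. If such prescribing is independent of the defined outcome, the coded rate is 1 − (1 − p)(1 − q). Power uses 424 × 0.9 = 381.6 per arm and the normal approximation without continuity correction.

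| Added q, usual care / PAAP | Coded rates | RR | Risk difference (points) | Power |
|---|---|---|---|---|
| 0 / 0 | 2.0% v 7.0% | 3.50 | 5.0 | 92% |
| 1% / 1% | 2.98% v 7.93% | 2.66 | 4.95 | 86% |
| 2% / 2% | 3.96% v 8.86% | 2.24 | 4.9 | 79% |
| 5% / 5% | 6.9% v 11.65% | 1.69 | 4.75 | 62% |
| 10% / 10% | 11.8% v 16.3% | 1.38 | 4.5 | 43% |
| 1% / 3% | 2.98% v 9.79% | 3.29 | 6.8 | 97% |

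Equal additions pull the relative risk towards 1. If the added prescriptions are commoner after de-labelling, as in the last row, the risk difference rises from 5.0 to 6.8 points while the relative risk changes little.

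Restoring the listed-infection condition leaves the sample size at 848, because that number was built on the defined outcome.

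**The case against.** The strongest reply is that the definition stands directly above the coding rule and is repeated in section 4.1 and Appendix I, so a careful analyst would apply both. For the main source this largely works: ISPRIMARYEVENT carries the listed-infection restriction, the coding sentence itself requires a penicillin, and the antibiotic-prescription outcomes in section 2.1.2.3 already name ABXNAME and a penicillin/non-penicillin split. That stands, and it confines the problem mainly to hospital reports and calls. It does not remove it: the rule never requires both conditions for one prescription and states no filter for the other sources.

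Two stronger readings are tempting, and the document supports neither.

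- A reader might infer that ISPRIMARYEVENT alone would serve as the outcome, so that about 50% of each arm would be coded 1 and the relative risk would be about 1.0. This ignores the requirement, in the same sentence, for evidence of a penicillin.
- A reader might infer that listed infections treated with non-penicillins would leave the denominator, giving 2/52 v 7/57 and a relative risk of about 3.2. But 2.1.1 has only one route to a missing outcome, which needs withdrawn consent for notes review, and section 3.3 keeps all data as far as possible. The wording for 0 is unclear on these participants, but nothing licenses excluding them.

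It is also fair to say that section 2.3 recounts how the outcome was changed, so its primary-care wording is a matter of consistency and not a rival definition.

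**Conclusion.** The point holds in this form: the derivation rule for the primary outcome contradicts the definition it is meant to implement. A participant given a penicillin only for an unlisted infection, found in a hospital report, is 0 by definition and 1 by the rule. For SystmOne/notes data the infection restriction is present through the flag, but its combination with drug identity is left unstated.

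The size cannot be fixed from the SAP. Under assumed equal additions of 1% to 10% in both arms, the relative risk falls from 3.5 to between 2.7 and 1.4. Under unequal additions the risk difference may instead be inflated. These figures rest on the SAP's 50%, 4% and 14%, on independence of the two kinds of prescribing, and on unlisted penicillins being counted at the assumed rates. If few are found in hospital reports and calls, the effect will be small. No stated figure in the SAP is wrong, and the sample size stands.

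The rule should be corrected because it governs the only confirmatory test and the correction is cheap.

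**What to change.** Replace the coding sentences in section 2.1.1 along these lines:

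- **Code 1** if, on any listed source, the same prescription (a) is a penicillin by drug name (for example ABXNAME with the existing drug classification), (b) is for an Appendix II infection, and (c) falls within 12 months of randomisation. For (b), use ISPRIMARYEVENT = yes for SystmOne/notes, and check the indication against the notes for calls and hospital reports.
- **Code 0** for all other participants, stating explicitly that this includes those with listed infections treated only with non-penicillins.
- **Missing:** keep the existing rule.

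State one care-setting scope and one list of sources in 2.1.1, 2.3 and Appendix I.

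The cost is a few sentences and one derivation line, with no change to the sample size. The SAP does not say whether hospital prescribing reports record the indication. If they do not, penicillin records found only there or on calls need a check against notes, which the trial already reviews. The revision should be dated before allocation is unblinded and reported under section 12.
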